## **STUDY OBJECTIVES**

**PRIMARY** - The primary objective of this study is to determine if the application of lower frequency (35kHz to 45kHz) ultrasound energy to the waist/abdominal region of the human body is capable of effecting a reduction in the amount of subcutaneous adipose cells and/or tissue to an amount of at least 1 inch and to a statistically significant level. Determination of the reduction in this adipose tissue is achieved via measurement of the body circumference that includes the abdominal area that was treated, and comparing measurements prior to the initial treatment with measurements after the entire treatment regime is concluded. Per the proposed clinical mechanism of action, the disrupted tissue is cleared by the lymphatic system which facilitates excretion or elimination of the disrupted tissue contents. Having been eliminated, the patient should exhibit a reduction in waist circumference. For this objective to be successfully achieved, a reduction in waist circumference of at least one inch must be demonstrated at a point of 12 weeks after the last of three treatment sessions has been applied.

**SECONDARY** - The secondary objective of this study is to assess the safety of this device. Assessment is made by having the patient rate the treatment experience and report any symptoms, side effects, or associated abnormal conditions. Additional assessment is made by the investigators to qualitatively confirm if visually detectable abnormal conditions (example: edema) are presented following the treatment. Success is determined by whether the patients indicate that any discomfort experienced during the treatment, and following the treatment that are directly attributable to the treatment, along with an absence of side-effects or abnormal conditions directly attributable to the treatment, create a risk/benefit condition where the benefit of treatment is regarded to outweigh the risks and temporary discomfort. Quantitatively, the benefit is regarded to outweigh the risk when: 1) No patients report a pain rating of 4 or higher on the Stanford Pain Scale, 2) No patients exhibit any side effects or abnormal conditions at the conclusion of the final treatment, and 3) No patient who was included in the Test group reports that the treatment regimen was unsuccessful.

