### **Study configuration**

This study is designed as a single-arm study. All eligible candidates shall be enrolled to undergo treatment by the device according to the procedure and protocol that are discussed herein. This approach is consistent with other studies that have been done with similar devices where the primary objective of waist circumference reduction was also intended.

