#### TREATMENT (total time of activity, 14-18 weeks - 4-6 weeks for the 1st, 2nd, and 3rd treatment applications, and 12-14 weeks following the 3rd treatment for follow-up visit):

##### Individual Treatment Session (approximately 70 minutes)

###### Prior to the Treatment (about 10 minutes):

- The patient is scheduled to arrive at the study site to undergo a treatment.
- The date of the treatment and the time of arrival will be documented in the treatment session record.
- During the first treatment only: The patient is given the Q-Pre Survey to fill out.
- The assigned pre-treatment investigator measures the waist circumference of the patient and documents this in the Pre-Treatment record, with these measurements being made by the blinded assessment clinician as described in the Measurement Tools and Methods section of this protocol.
- Prior to Treatments 2 and 3, the patient will be asked for the study diary, and the pre-treatment investigator shall review the diary and the patient's previous post-treatment Anticipated Effects and Adverse Event forms and discusses with the patient the items that are recorded about any abnormal body functions or observations that may be relevant to the treatment. If any are indicated, these will be documented in the patient record. Additional record shall be made by the investigator as to whether past events and observations have been resolved or are still unresolved.
- The patient is moved to the treatment area.

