**Post-Treatment Assessment (approximately 15 minutes):**

- The Post-Treatment assessing investigator observes the treated area for any redness, edema, swelling, or other indications specifically called for in the Anticipated Effects treatment record. The patient is asked for any unexpected sensations, for example sensations of high heat or of a "pins and needles" tingling effect in the tissue. These anticipated effects are documented in the treatment session record. Un-anticipated effects are recorded in the Adverse Event form.
- The patient is presented with the Stanford Pain Scale chart and asked to rate their overall pain and discomfort during the treatment. This is documented in the treatment session record.
- A waist circumference measurement of the abdominal region is made using the constant-tension tape measure. This measurement is recorded in the Post-Treatment Measurement record.
- The patient is provided with a study diary form, and instructed to document in the diary any unusual sensations, events, or bodily responses and to bring the form with them for the next visit.
- At the final treatment session only, the patient is provided with the Q-Post Survey to fill out.
- The patient is then scheduled for the next study session, and then excused.

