**FOLLOW-UP (approximately 15 minutes):**

- The patient is scheduled for and arrives at the study site at the appropriate time points 1, 4, or 12 weeks after the final treatment.
- The date of the visit and the time of arrival will be documented Post-Assessment Measurement and Anticipated Effects forms.
- For the 1-week and 4-week visits, the patient fills out the WaistQ-Post Survey. For the 12-week follow-up, the WaistQ-12 Survey is filled out.
- The patient will have their waist circumference measured and documented by an investigator assigned to the post-treatment measurement and assessment activity, as described in the Measurement Tools and Methods section of this protocol. The patient will be asked for the study diary, and the investigator shall review the diary and discuss with the patient the items that are recorded about any abnormal body functions or observations that may be relevant to the treatment. If any are indicated, these will be documented in the patient record. The

investigator will also review observations and adverse events documented in previous sessions and discuss these with the patient. Additional record shall be made by the investigator as to whether past events and observations have been resolved or are still unresolved.

- For the 4-week or 12-week follow-up visits, the patient is provided with a study diary form, and instructed to document in the diary any unusual sensations, events, or bodily responses and to bring the form with them for the next visit. The patient is then scheduled for the 4-week or 12-week follow-up visits as appropriate.
- At the 12-week follow-up, additional review is made of the patient's Medical History and Medication forms and any new content for these forms is noted therein and discussed with the patient. If the 12-week follow-up visit is concluded and Adverse Event forms indicate any unresolved adverse results for the patient, additional follow-up is scheduled as appropriate until all adverse results are concluded.

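### The numbered rule for the safety objective fails on a single report of perceived inefficacy and counts side effects at only one time point

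*Combined protocol and SAP*

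**What the plan says.** STUDY OBJECTIVES first describes success on the secondary objective in words: benefit should outweigh risk and temporary discomfort, with an "absence of side-effects or abnormal conditions directly attributable to the treatment". That sentence sets no time limit. A numbered rule then makes it quantitative through three conditions joined by 'and'. The first concerns pain ratings. The second is "No patients exhibit any side effects or abnormal conditions at the conclusion of the final treatment". The third is "No patient who was included in the Test group reports that the treatment regimen was unsuccessful". No other section gives a tolerance or a wider window.

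The data collected are broader than the rule:

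- After every session the post-treatment assessor "observes the treated area for any redness, edema, swelling, or other indications specifically called for in the Anticipated Effects treatment record" (Post-Treatment Assessment).
- Before sessions 2 and 3 the diary and earlier forms are reviewed, and "Additional record shall be made by the investigator as to whether past events and observations have been resolved or are still unresolved" (Prior to the Treatment). FOLLOW-UP repeats this review at 1, 4 and 12 weeks.
- Several surveys might supply the answer that the third condition needs. "At the final treatment session only, the patient is provided with the Q-Post Survey to fill out" (Post-Treatment Assessment). The WaistQ-Post form follows at 1 and 4 weeks, and "For the 12-week follow-up, the WaistQ-12 Survey is filled out" (FOLLOW-UP).

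**The concern.** A decision rule for safety should respond to harm and to little else. This one departs from that in both directions.

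The third condition measures whether the patient thinks the treatment worked. A device that hurt nobody would still fail its safety objective if one patient was disappointed. Because no survey or visit is named, the answer could come from the last session, 12 weeks before the efficacy time point, or from any follow-up visit.

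The second condition looks at one moment. Effects that appear during follow-up are outside it. A brief local reaction just after session 3 is inside it, although ADVERSE INTERACTIONS lists local inflammation and edema as anticipated.

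The rule is the only quantitative route to the safety conclusion. The sentence and the rule could therefore give different answers on the same data, and the report could defend either.

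**Working it through.** **Third condition.** The plan states no pass probability or report rate for its safety rule, so there is no figure to reproduce. Inputs:

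- n = 40 (minimum completers) and n = 50 (recruitment), from Sample size.
- n = 20, an assumption: half of 40, in case the Test group is one of two equal groups.
- p, the true proportion of patients who would call the regimen unsuccessful. This is an assumption, so a range is shown.
- Independence between patients, also assumed.

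Chance that a zero-count condition fails: 1 − (1 − p)^n. For n = 40 and p = 0.01: 1 − 0.99^40 = 1 − 0.669 = 0.331.

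Rate at which failing and passing are equally likely: 1 − 0.5^(1/n). For n = 40: 1 − 0.5^(1/40) = 0.0172.

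| n | fails at p = 1% | at 2% | at 5% | break-even p |
|---|---|---|---|---|
| 20 | 18.2% | 33.2% | 64.2% | 3.4% |
| 40 | 33.1% | 55.4% | 87.1% | 1.7% |
| 50 | 39.5% | 63.6% | 92.3% | 1.4% |

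The larger the trial, the more likely the condition is to fail at the same report rate.

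**Second condition.** No arithmetic applies. The table compares the descriptive sentence with two readings of the condition. The plain reading is what is seen at the check just after session 3. The looser reading is anything seen up to the end of session 3.

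| Effect | Descriptive sentence | Plain reading | Looser reading |
|---|---|---|---|
| Attributable, after session 1 or 2, resolved before session 3 ends | counts | does not count | counts |
| Brief anticipated reaction just after session 3 | counts if directly attributable | counts; fails the rule | counts; fails the rule |
| Attributable, first seen at 1, 4 or 12 weeks | counts | does not count | does not count |

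The third row does not depend on the reading. The first row turns on the word 'at'.

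**The case against.** The strongest defence is that the plan asks for a benefit-risk judgement, so a benefit term belongs in the rule and zero tolerance is a conservative choice open to the sponsor. The first half stands: a benefit term was plainly intended, and simply deleting the third condition would leave the lead-in about benefit outweighing risk with nothing on the benefit side. The lead-in therefore has to change too. The defence does not explain why one opinion about efficacy should decide an objective defined as safety.

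A second defence is that the second condition targets effects still present when the treatment course ends, since the plan accepts temporary discomfort. Passing over effects that cleared earlier might then be deliberate. Effects that begin during follow-up would still be missed.

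Some stronger readings are tempting but not supported:

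- *The rule abandons attribution.* The second condition does not repeat the attribution wording, but it puts the preceding sentence into numbers and may inherit it. What is established is that the two are worded differently.
- *Patients withdrawn early are outside the rule.* This follows only if the final treatment means session 3 and not the patient's own last session.
- *The plan itself predicts unsuccessful reports.* The remark in Sample size that some patients may not respond supports the SD for circumference. It does not forecast survey answers, and the survey items are not in the text.
- *Safety data go uncollected.* They are collected, followed to resolution and audited (Prior to the Treatment, Post-Treatment Assessment, FOLLOW-UP, Monitoring).

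**Conclusion.** The point holds for the numbered rule and no further. One report of an unsuccessful regimen fails the safety objective without any harm, and the source of that report is undefined. Side effects first seen in follow-up do not enter the second condition on any reading; on the plain reading, neither do those that resolved after session 1 or 2, while a short anticipated reaction after session 3 fails the rule.

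The size depends on an unknown report rate. The calculated failure chances show how fragile a zero-count condition is; they do not forecast this trial. They rest on independence, on the assumed rates and, for 20 patients, on an assumed equal split.

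This should be corrected, but it concerns a secondary objective and leaves the primary analysis untouched. Two neighbouring matters are outside this point. The pain condition is also zero-tolerance with no visit named. The reference to a Test group conflicts with "This study is designed as a single-arm study" in Study configuration, while the title page, the synopsis Statistical Methods and Sequence and duration of study period refer to a control or to study groups; that must be reconciled separately.

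**What to change.** 1. In STUDY OBJECTIVES, take the third condition out of the safety decision. Report the proportion calling the regimen unsuccessful as a patient-reported efficacy result, with the survey and visit named. Reword the lead-in so that the numbered rule is a safety rule and benefit is judged separately.
2. Make the second condition cover side effects and abnormal conditions at all three sessions and at the 1-, 4- and 12-week visits, in every patient treated at least once, including those who stop early. Tabulate patients by anticipated and unanticipated effect, and by study group if there is more than one, with exact 95% confidence intervals. If a pass/fail label is kept, the sponsor sets its limit in advance.
3. Use the same attribution wording in the sentence and the rule. If attribution is used, state who judges it and record it on the Anticipated Effects and Adverse Event forms.
4. State that the exclusion and fill-in rules in Data quality assurance and Statistical methods planned apply to waist circumference and not to safety data. Neither section now limits them in that way.

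The cost is rewording, one table and possibly a new form entry, since no section describes a field for attribution. More events will be counted, and the safety conclusion becomes an estimate with an interval unless a limit is set beforehand.

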## INVESTIGATIONAL PLAN

### Device description and settings

The Ultimate Contour device is a portable device that consists of a single central unit which houses all of the device electronics. The device features a fold up touchscreen that shows the device's operating condition and allows the operator to select the device's functional parameters. A single external, detachable power cord connects the device to an ordinary electrical outlet. The device contains an internal power supply that is auto switching to the input voltage and input frequency (100-240VAC, 50-60Hz). The device includes a single, detachable output cable. The operator attaches the ultrasound treatment handpiece to the device. The device is designed to allow application of RF energy via separate specifically designed handpieces, but the application of RF energy is not within the scope of this study. The device is capable of sensing if a handpiece is attached and to identify which handpiece is attached, in order to prevent any inappropriate power from reaching the handpiece or prevent the device from being configured in an inappropriate manner.

After attachment of the handpiece, the operator selects which treatment type (US or RF) is to be done. The device then presents only two parameters for operator to adjust: the duration of the treatment, and the relative intensity of the applied energy. The duration can be selected from 10, 20, 30, or 40 minutes duration. The intensity is selected from a comparative rating Level of "1, 2, 3, or 4", with Level 4 being the maximum energy level the device can output and Levels 1 through 3 being at staggered levels less than the maximum. Once the settings are selected, the operator places the device into a Ready state. At this point, the handpiece is placed in contact with the skin and the operator presses a button on the screen to Activate the handpiece. The unit applies energy to the handpiece at the selected intensity Level and the unit begins to count down from the selected time duration. Generally, the operator allows the device to operate until the selected time elapses, at which point the device automatically returns to the Ready state and beeps to inform the operator the cycle is complete. The operator may also stop the treatment at any time, either by pressing the stop button on the screen or activating a separate emergency stop button located on the device. During treatment, the device monitors the temperature of the handpiece (and by contact, the temperature of the skin) via temperature sensors located in the handpiece and in direct contact with external metal surfaces of the handpiece that contact the skin. If excessive temperature is measured, the device halts operation of the handpiece. For the purposes of this study, the device will be set at a treatment time of 30 minutes and an intensity level of 4.

Adjunctive activities associated with the treatment will also be performed. These included conversation with the patient about what to expect during the individual treatments and overall outcomes of the entire regimen, as well as instructions to the patient at the conclusion of the study regarding care and proper lifestyle habits. All of these adjunctive activities are described in the operator's manual for the device, and the clinicians will be instructed on the presence of these consultative activities in the manual and the execution of these activities for the purposes of this study.

### Patient population

The population for this study shall consist of adults age 18 and over. Recruiting efforts shall focus on obtaining a reasonably even number of male and female patients and to include patients exhibiting a body mass index (BMI) of 25 or higher. No concern or focus will be given regarding the ethnicity of the patients, although a wide range of ethnicities would be beneficial. Patients will be evaluated relative to the inclusion and exclusion criteria indicated below. A recruitment target of a total of 50 patients is established. During recruitment, each candidate will be assigned a test subject number for identification purposes.

### **Study blinding**

Blinding for this study shall primarily be at the level of the study investigators, whereby the investigator performing the treatment shall not be the same as the investigator who makes the pre-treatment assessment, who is not the same as the clinician performing the post-treatment assessment of the patient for immediate adverse effects. In other words, at any given time while a patient is present at the study site, there will be a minimum of three clinicians present at the site, and each respective clinician shall be assigned to one of the three activities (pre-assessment, treatment, or post-assessment) for the duration of that day's activities. Patient forms shall be designed such that dedicated forms are provided for each of these three activities, and the forms of any one particular activity (for example, the pre-treatment assessment) are not provided to or made available during the other activities of the patient's visit (ex. provided during the post-treatment assessment).

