**Efficacy of Low-Frequency, High-Intensity Ultrasound  
for Reduction in Subdermal Adipose Layers**

Device Investigated: Ultimate Contour Body Sculpting Device

Indication Studied: Application of ultrasound for non-invasive waist circumference reduction.

A randomized, blinded comparison of waist circumference reduction of an active test group vs. a placebo control in adults.

Sponsor: CAO Group, Inc.

Protocol ID: 005-00036-8

Development Phase: Performance Validation

NCT ID: Not Yet Assigned

Anticipated Initiation Date: 15 December 2019

Anticipated Completion Date: 1 May 2020

Document Date: 10 October 2019

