### **Sequence and duration of study period**

Patients will be scheduled according to each one's availability for the first of three treatment sessions. After each particular treatment, the patient will be scheduled for the next visit, with it being preferred that subsequent treatments occurring between 6-8 days into the future of the present treatment. Each patient is to receive 3 treatment sessions, with each session featuring the same device settings and conditions of application relative to which study group the patient is assigned to. Overall, the study treatments are anticipated to take about 6 weeks to accomplish. The patient is recalled 1 week, 4 weeks, and 12 weeks after the last treatment for follow-up evaluation.

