#### Monitoring

The study shall be monitored in the following manner:

- Training and Initial Inspection: The sponsor shall visit the study site and shall conduct an inspection of the site to determine that the site is adequate and appropriate for the activities described in this protocol. In particular, attention shall be given to ensuring that separation of treatment and the two assessment activities are accommodated to ensure patient and staff blinding is maintained, and that patient safety is ensured. Training shall be conducted for the investigators and staff regarding the study protocol, methods of measurement, and operation of the device.
- Informed Consent: The sponsor shall obtain copies of the signed informed consent forms prior to delivery of study devices.
- Surprise Inspection: At least twice during the course of study treatments, an independent third-party shall conduct a surprise inspection of the study site while treatments are being conducted, to review that the protocol is being followed, confirm that protection of human subjects is being employed, and ensure that treatment records are properly filled and maintained. Since the total duration of the device treatment period is anticipated to be only 4-6 weeks, the mandated 2 surprise visits are considered appropriate. If records or actions of investigation staff are found to be inconsistent, additional site inspections and possible additional training shall be employed.
- Collection of devices and records: Once all device treatments are completed, the sponsor shall retrieve the study devices and obtain copies of all treatment records. The sponsor shall review the patient records, and make especial note of adverse interactions contained in the records.
- Follow-up Records: At the conclusion of the follow-up visits, the sponsor shall collect the patient records from the follow-up visit. The sponsor shall compare and confirm that all adverse

interactions that have been documented have been resolved at this point. If any adverse interactions are still unresolved, the sponsor shall work with the investigator to continue follow-up with the affected patients to achieve resolution.

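### The plan calls the waist reading and the patients blinded, but it describes no sham session, and the 12-week waist is read by the role that inspects treated skin and reviews adverse events

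*Combined protocol and SAP*

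**What the plan says.** **Claims of blinding.** The title page announces "A randomized, blinded comparison of waist circumference reduction of an active test group vs. a placebo control in adults". The Synopsis (Methodology) names a blinded, independent evaluator for baseline weight and height, with the waist measurement in the same sentence, and again for the post-treatment skin check. The Prior to the Treatment section describes the waist readings "with these measurements being made by the blinded assessment clinician". The Monitoring section asks the sponsor to inspect the site to "ensure patient and staff blinding is maintained".

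**Design.** Study configuration states: "This study is designed as a single-arm study". Sequence and duration of study period nevertheless sets conditions "relative to which study group the patient is assigned to". Application of the Treatment describes one procedure, with the device active at fixed settings.

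**Separation of roles.** Study blinding assigns pre-assessment, treatment and post-assessment to different clinicians for the day. It adds that "the forms of any one particular activity (for example, the pre-treatment assessment) are not provided to or made available during the other activities", and the sentence goes on to limit this to the patient's visit.

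**Access to reaction history.** Before Treatments 2 and 3 the pre-treatment investigator reviews the diary and the patient's "previous post-treatment Anticipated Effects and Adverse Event forms and discusses with the patient the items that are recorded". In Post-Treatment Assessment, the post-treatment investigator inspects the treated area, asks about sensations and records the pain score; a waist reading is taken in the same step. FOLLOW-UP gives the waist readings at 1, 4 and 12 weeks to that same post-treatment activity, and also has the investigator "review observations and adverse events documented in previous sessions and discuss these with the patient".

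**The concern.** The primary endpoint is a hand-held tape reading, taken at the start and at 12 weeks. The tape's tension is controlled, but its placement and the moment of reading depend on the clinician. Blinding is the plan's stated protection against that influence.

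Two things undercut it. First, patients cannot be blinded by a plan that describes only the active procedure. Second, the role that takes the decisive 12-week reading is the one whose other duties bring it closest to the signs of treatment: redness, swelling, pain and reported events. If some patients receive a placebo session, those signs can show who was treated, and a reader who knows this can shade the tape in one direction. If nobody does, the report would still describe as blinded a reading that cannot be.

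**Working it through.** **1. What would have to exist for the claims to be true.**

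| Claim | Means described in the plan |
|---|---|
| Placebo control (title page) | None. No sham handpiece, placebo setting, randomization or concealment appears; Study configuration treats all eligible candidates |
| Patient blinding (Monitoring) | None. The single session procedure is active treatment |
| Blinded waist reading (Synopsis, Prior to the Treatment) | Staff separation by day, separate rooms, and a within-visit rule on forms |

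**2. Who takes the readings that decide the study.** The Synopsis and the primary objective define success by the change from the initial measurement to week 12.

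- Initial reading: the pre-treatment role, before any effect record exists. It is not exposed to reaction history.
- Week-12 reading: the post-treatment role. That role has inspected skin and recorded pain after each of three treatments, and has reviewed diaries and events at weeks 1 and 4. Within the week-12 visit the waist is listed before the review, so that visit's review need not influence the reading; the earlier ones can.

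**3. What the rule on forms covers.** It applies within one visit. The pre-treatment review before Treatments 2 and 3 uses forms from a previous visit, so the two sections conflict only if the rule is meant to span visits. The readings at Treatments 2 and 3 are not part of the primary change. At week 12 the effect and event records come from the post-treatment reader's own activity, so the rule does not withhold them. It therefore neither forbids the exposure in step 2 nor prevents it.

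**4. Illustration of size.** The documents give no observer-error figure, so the shift is assumed.

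*The plan's own figure first.* Sample size uses n = 2(Zα + Zβ)²σ²/d² with Zα = 1.96, Zβ = 0.84, σ = 1.50 and d = 1.0:

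2 × (2.80)² × 2.25 / 1 = 35.28, rounded up to 36.

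The stated 37 agrees with the exact two-sample t calculation (power 79.7% at 36 per group, 80.8% at 37). The formula is for two groups and gives n per group.

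*Illustration.* Assume a control is kept, 40 completers split 20 and 20 (the plan gives no ratio), SD 1.50, no true effect, and a reading shift b favouring treated patients.

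- Standard error of the difference = 1.50 × √(2/20) = 0.474 inch.
- Noncentrality = b / 0.474: 0.42 for b = 0.2 and 0.63 for b = 0.3.
- Critical t on 38 df, two-sided 5%: 2.024.

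| Assumed shift (inch) | Chance of significance favouring treatment |
|---|---|
| 0 | 2.5% |
| 0.2 | 6.1% |
| 0.3 | 9.0% |

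Over a wider assumed range of 0.1 to 0.5 inch, the two-sided rate goes from 5% to about 5.5% and 18.4% (normal approximation). These rates concern significance only. The primary objective also requires a reduction of at least 1 inch, which they do not cover.

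**The case against.** The plan does contain real safeguards. Treatment and measurement take place in separate rooms with different staff, and treatment clinicians may not serve as assessors. These stand, and they keep the person who delivers the energy away from the tape. They do not keep the tape away from the person who inspects the skin.

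Roles are assigned by day, so the clinician who reads the waist at week 12 need not be the one who reviewed that patient's events earlier. That is true, but nothing in the plan prevents it from being the same person.

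Three stronger readings are tempting and are not supported:

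- *The assessors are made to read forms that the blinding section withholds, so the primary reading breaches the plan's own rule.* The rule is worded for one visit, the cross-visit review touches only Treatments 2 and 3, and the forms belong to the week-12 reader's own activity.
- *The leak matters equally whichever design is meant.* Reaction history can reveal allocation only if some patients are not treated. In a single arm every assessor already knows the patient was treated.
- *The bias can be sized by testing a single arm against zero change.* That joins a mechanism that needs two groups to a test with one, and it ignores the 1-inch requirement.

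**Conclusion.** The concern holds in limited form. The patient-blinding claim has no support anywhere in the procedures. The 12-week reading is assigned to a role exposed to skin findings, pain scores and earlier events, so the plan does not justify calling it blind.

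The consequence depends on the design, which the title page and Study configuration describe in opposite ways. With a control, the exposure can disclose allocation. Under the assumed 0.2 to 0.3 inch shift, 20 per group and SD 1.5, favourable-direction false positives rise from 2.5% to about 6% to 9%. With a single arm there is nothing to conceal, and the fault lies in the description; a reader unaware of reactions and earlier readings would still be good practice.

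The overlap between Study blinding and Prior to the Treatment is a secondary tension to reconcile. The finding on roles and claims rests on the text alone; only the illustration depends on an assumed bias.

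**What to change.** 1. In Prior to the Treatment and in FOLLOW-UP, assign the diary and event review to the principal investigator, who already has the duty of discussing adverse interactions under Study staff, and place it after the waist has been recorded. This also removes the tension with the rule on forms.
2. Have the follow-up waist read by an existing assessment clinician who did not carry out that patient's post-treatment skin inspections and who has no access to event forms, diaries or earlier waist readings. Simply passing the reading to the pre-treatment assessor would not do, because that role records the baseline.
3. Reconcile the title page with Study configuration. If a control is kept, describe what the placebo session consists of. If it is not, delete the patient-blinding claim in Monitoring and the blinded wording on the title page, in the Synopsis and in Prior to the Treatment.

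The cost is wording, a few minutes of the principal investigator's time per visit, and some scheduling of existing staff. These changes to roles and wording add no patients or visits.
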